5 STUDY POPULATION

5.1 Inclusion Criteria

In order to be eligible to participate in this study, an individual must meet the following criteria:

1. Aged 3 years and older.
2. Must be eligible to receive (based on official FDA authorization or approval) and scheduled to receive or have already received a COVID-19 vaccine outside of this study.
3. Must meet the definition of affected participant or control participant:
 - a. Affected participants must have evidence of a primary or secondary immune deficiency or dysregulation under another NIAID protocol or as documented by an outside physician.
 - b. Control participants are healthy volunteers that do not have evidence of a primary or secondary immune deficiency or dysregulation and may include unaffected relatives of affected participants.
4. Ability to provide informed consent.
5. Willing to have blood samples stored for future research.
6. Able to proficiently speak, read, and write English.

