5.7 Strategies for Recruitment and Retention

Immunodeficient individuals will be recruited from NIAID protocols that evaluate primary or secondary immune deficiencies. Potential subjects will be identified by discussion between the study teams and review of medical and research records if necessary. They may also be referred from community practitioners who see this population.

Healthy adult volunteers will be recruited through the NIH Clinical Research Volunteer Program, the Office of Patient Recruitment, MMG Patient Recruitment, ResearchMatch, or BuildClinical. Volunteers will also be recruited from existing NIH protocols, including but not limited to protocol 18-I-0101 (“Sample Collection From Healthy Volunteers For Assay Optimization”), 93-I-0119 (“Detection and Characterization of Host Defense Defects”), 18-I-0041 (“Investigating the Mechanistic Biology of Primary Immunodeficiency Disorders”), 11-I-0187 (“Natural History of Individuals with Immune System Problems that Lead to Fungal Infections”), and 17-I-0122 (“NIAID Centralized Sequencing Protocol”). Healthy relatives of immunodeficient participants can be recruited for participation as controls if they meet enrollment criteria.

An IRB-approved recruitment email will be distributed to potential participants, and flyers with study team contact information will be posted throughout the CC and provided to community practitioners to share with potentially eligible patients. We may also conduct outreach activities with local groups involving patients with immune deficiencies (eg, support groups and patient advocacy groups). Interested individuals may also contact the study team directly via email.

A pre-screening phone call will be conducted with individuals who express interest, for an initial discussion of eligibility (including any past SARS-CoV-2 testing) and scheduling prior to the screening visit.

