8.3 Sample Size Justification

The sample sizes proposed in this protocol were set based on the primary objectives of this study, which are to characterize the immune response to COVID-19 vaccination as measured by enzyme-linked immunosorbent assay (ELISA) anti-S-2P and anti-RBD IgG titers at approximately 3-4 weeks following each vaccination and in long-term follow-up. The following sample size determination is based on results of the phase 1 dose escalation study of the Moderna mRNA vaccine.⁹ Fifteen participants received a dose of 100 ug of vaccine, and the means and standard errors of the log₁₀ antibody titers at the nearest timepoints to the times at which we propose to collect samples are summarized in the table below.

Target	Study day	Mean log ₁₀ -titer (Standard error)
S-2P	29	5.04 (0.28)
	56	5.89 (0.19)
RBD	29	4.97 (0.38)
	56	5.57 (0.27)

We assume that healthy volunteers in the upcoming trial have similar immune responses to those reported in the Moderna Phase I trial, and that immune deficiency/dysregulation shifts the log₁₀-titer distribution among individuals with immune deficiency/dysregulation but does not change the standard deviation of the responses. We also suppose that healthy volunteers and immune deficient/dysregulated individuals have similar baseline distributions, which is reasonable as both groups are naïve at baseline. As we were unable to obtain specific estimates of antibody responses to the Pfizer vaccine that could be used to estimate the sample size for this study, we are left to assume that responses to the Pfizer vaccine are similar to the Moderna vaccine.

Using the estimates from the Moderna study, we calculate, and plot below, the smallest differences in mean log-titers that we would be able to detect using a two-sided two-sample t-test with either 80% or 90% power while controlling the type I error rate at $\alpha=0.05$ as a function of sample size. We also display the widths of 95% confidence intervals for a difference in mean log-titers. As an example, a sample size of 20 immune deficient/dysregulated individuals and 20

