healthy volunteers should be sufficient to detect a true difference in mean anti-RBD log-titer of 0.4 at day 29 with 90% power, or a true difference of 0.35 with 80% power, while controlling the type I error rate at $\alpha=0.05$. We would also expect the width of a 95% confidence interval for the difference in mean log- titers to be approximately 0.35 units. It is also useful to consider the minimum detectable standardized effect size, also shown below, as antibody responses to other vaccines may differ from responses to the Moderna vaccine. Continuing with our example, a sample size of 20 participants per arm would be sufficient to detect a 1.05 standard deviation difference with 90% power using a two-sided two-sample t-test while controlling the type I error rate at $\alpha=0.05$.

[figure not shown]

Figure 2. Sample size estimates for primary endpoint. **A)** Lines represent number of participations required in each group and the smallest detectable differences in mean log-titers using a two-sided two-sample t-test with either 80% or 90% power while controlling the type I error rate at $\alpha=0.05$. **B)** Widths of 95% confidence intervals for a difference in mean log-titers. **C)** Number of participants required in each group to detect differences in standardized antibody effect size using a two-sided two-sample t-test with either 80% or 90% power while controlling the type I error rate at $\alpha=0.05$.

While it is hard to generalize antibody responses across the many immune conditions in this study given the phenotypic heterogeneity between and within diseases, patients in the following groups would generally be expected to have poor antibody responses to vaccination:

- Defects of cellular and humoral immunity (n=20) (e.g. RAG, DOCK8, adenosine deaminase [ADA], nuclear factor-kappa B essential modulator [NEMO])
- Predominantly antibody deficiencies (n=40) (e.g. X-linked agammaglobulinemia [XLA], CVID, activated PI3K delta syndrome 1/2 [APDS1/2], Ras-related C3 botulinum toxin substrate 2 [RAC2], caspase recruitment domain-containing protein 11 [CARD11], gain-of-function [GOF])

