8.4.1 Analysis of the Primary Endpoint

Log transformed antibody measurements will be modeled within a mixed model repeated measures (MMRM) framework, which is a longitudinal mixed model with fixed effects for (categorical) timepoint, immune deficiency/dysregulation, and the interactions of timepoint with immune deficiency/dysregulation and timepoint with baseline measurement, along with possible adjustment other covariates, such as age and sex. In this framework, we also include correlated subject-level random effects for each timepoint to account for clustered data. This also allows us to estimate the correlation between antibody responses to the first and second doses of vaccine. MMRM models are an appropriate tool for assessing response profiles in longitudinal studies where missing data is expected and it is appropriate to assume that data are missing at random conditional on observable covariates.^{13,14} The previous sample size justifications based on two-sample t-tests are likely to be slightly conservative as we expect the MMRM framework to make more efficient use of the data. Models will either be fit using the 'nlme' package in R, or, if a Bayesian formulation is deemed to be preferable for the purpose of incorporating prior information, can be fit using the 'brms' and 'rstanarm' packages.

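### The plan permits related participants but models clustering only within the subject; if relatives enrol, patient v related-control standard errors tend to be too large and those for groups holding several family members too small

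*Combined protocol and SAP*

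**What the plan says.** Section 5.1 states that controls "may include unaffected relatives of affected participants", and section 5.7 adds: "Healthy relatives of immunodeficient participants can be recruited for participation as controls if they meet enrollment criteria". The synopsis says the same. None of these places gives a cap or an expected number. The inclusion and exclusion criteria (5.1, 5.2) neither mention nor exclude a second affected member of a family.

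The primary model in 8.4.1 is a mixed model for repeated measures on log titer, with age and sex as possible covariates. Its provision for dependence is: "we also include correlated subject-level random effects for each timepoint to account for clustered data". Section 8.4.2 compares adverse-event incidence by regression, again with optional covariates, and names no clustering term. No family identifier, family effect, cluster-robust standard error or analysis restricted to unrelated participants appears.

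Section 8.3 sizes the study "using a two-sided two-sample t-test with either 80% or 90% power", which takes all participants as independent.

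**The concern.** Many of the disorders listed in the background are inherited, and patients are recruited partly from existing NIAID protocols, so families are a natural source of both patients and controls. Relatives share genes and often household exposure, so their responses to vaccination may be correlated. A subject-level random effect captures correlation between one person's visits. It does not capture correlation between two people.

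The consequence depends on where the relatives sit. Two relatives on opposite sides of a contrast have a positive covariance that should be subtracted from the variance of the difference. Ignoring it makes the interval too wide and wastes precision. Two relatives in the same group carry less information than two unrelated people. Ignoring that makes the group's interval too narrow. At stake is the width of the intervals in the within-group and between-group analyses of section 8.4, and of those for adverse events.

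**Working it through.** **1. The plan's own figure.** Section 8.3 takes "a sample size of 20 immune deficient/dysregulated individuals and 20" healthy volunteers and claims it can detect a difference in "mean anti-RBD log-titer of 0.4 at day 29 with 90% power, or a true difference of 0.35 with 80% power". The spread for anti-RBD at day 29 is 0.38. The table labels it a standard error, but the power statement uses it as a standard deviation. An exact two-sided t-test with 38 degrees of freedom gives:

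- 90.0% power at 0.40
- 81.0% power at 0.35
- 89.9% power at 1.05 SD, against the plan's claim to "detect a 1.05 standard deviation difference with 90% power"

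The figures reproduce, under independence.

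**2. Inputs and assumptions.** Group sizes come from section 8.2: 40 for predominantly antibody deficiencies and 120 healthy volunteers (the synopsis says 100). The following are assumptions, because the documents give no values:

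- family correlation ρ of 0.1 to 0.5
- share q of a group in same-group sibling pairs of 20% to 40%
- P patient-control related pairs, covering 20% to 100% of the patient group

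For scale, one sibling pair is already 20% to 40% of a group of 5 to 10, the size section 8.2 expects for complement deficiencies and for bone marrow failure. In a group of 40 the same shares mean 8 to 16 patients.

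**3. Siblings in the same group.** In units of the response variance, the variance of a group mean is (1 + qρ)/n instead of 1/n, so true SE / reported SE = √(1 + qρ).

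- q = 0.2, ρ = 0.1: √1.02 = 1.010. A nominal 5% test rejects 5.2% of the time.
- q = 0.4, ρ = 0.5: √1.20 = 1.095. It rejects 7.4% of the time.

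For the 40 v 120 contrast with siblings among the patients only, the reported variance is 1/40 + 1/120 = 0.03333.

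- Low end: 1.02/40 + 1/120 = 0.03383, ratio √1.015 = 1.007 (5.2%).
- High end: 1.20/40 + 1/120 = 0.03833, ratio √1.15 = 1.072 (6.8%).

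**4. Relatives as controls.** The variance of the difference falls by 2Pρ/(n₁n₂). For 40 v 120:

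- P = 8, ρ = 0.1: subtract 2 × 8 × 0.1/4800 = 0.00033. Ratio √0.99 = 0.995, rejection rate 4.9%.
- P = 40, ρ = 0.5: subtract 2 × 40 × 0.5/4800 = 0.00833. Ratio √0.75 = 0.866, rejection rate 2.4%.

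The patient group's own within-group variance does not contain this term, so its ratio stays at 1.000.

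**5. Both together.** Take 40% of patients in sibling pairs and P equal to half the patient group.

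- 40 v 120: ratio 1.002 at ρ = 0.1 and 1.012 at ρ = 0.5.
- 40 v 100: 1.04/40 + 1/100 − 2 × 20 × 0.1/4000 = 0.035, the same as the reported variance. The ratio is 1.000 at ρ = 0.5 too.
- 20 v 20: ratio 0.985 at ρ = 0.1 and 0.922 at ρ = 0.5.

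The within-group ratio in this mix is still 1.020 to 1.095.

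**6. Effect on the plan's example.** With 20 per group and 40% of the patients in sibling pairs, the ratio is 1.010 to 1.049. Power at 1.05 SD is then 89% to 87%, and the difference detectable with 90% power is 1.06 to 1.10 SD.

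**7. Change from baseline.** In a simulation of 20 v 120 (20,000 runs) with four sibling pairs and ρ of 0.3 to 0.5, the error rate was 5.5% to 6.1% between groups and 5.6% to 6.2% within the group. With 20 patient-control pairs instead, it was about 4.0% between groups and 4.8% to 5.0% within. When the family effect was equal at baseline and follow-up, it cancelled from the change score and both rates stayed near 5%.

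**The case against.** A reader might infer that standard errors are wrong throughout, both between and within groups. The documents do not support that. Relatives are allowed as controls, not required, and they are one recruitment source among several. Affected siblings are nowhere mentioned, so their presence is inferred from silence, and one planned group is secondary immunodeficiency rather than inherited disease. The route the documents do name, related controls, leaves the patient group's within-group standard error untouched and makes the patient-control contrast conservative. All of this stands.

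Larger effects can be produced: 60% of a group in sibling pairs at a correlation of 0.6 gives √1.36 = 1.17 and a 9.3% error rate, and 40 related pairs in a 50 v 120 contrast at 0.6 give a ratio of 0.85. Nothing in the documents supports inputs that extreme.

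A constant family effect would cancel from a change score. That stands as a limit, but section 8.3 supposes participants are naïve at baseline. A shared influence on the vaccine response would then appear only after vaccination and would not cancel.

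Finally, the study is exploratory, and a shift of a few percent in a standard error is unlikely to overturn a difference of one standard deviation, which is the plan's target. That limits the importance of the point. It does not justify an avoidable error in interval width where estimation is the main output.

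**Conclusion.** The point holds as a conditional one. Followed as written, the plan treats any related participants as independent. If relatives enrol, patient v related-control standard errors will tend to be too large, and standard errors for a group with several members of one family (affected siblings, or several related controls) will tend to be too small. In the patient-control contrast the two can offset, wholly for some mixes.

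Over the assumed ranges the effect is modest: at most about 10% on a within-group standard error, and up to about 13% excess in the true-to-reported sense (ratio 0.866) for a 40 v 120 contrast in which every patient has a related control. Whether any of this occurs depends on the number of relatives and the family correlation, which the documents do not give, and on the family effect differing between baseline and follow-up. This is a worthwhile low-cost improvement, not a threat to the study's conclusions.

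**What to change.** - Record a family identifier for every participant at enrolment. The documents do not say that kinship is captured, and it is harder to reconstruct later from coded data.
- In 8.4.1, add a family-level random intercept above the subject in the mixed model.
- In 8.4.2, use the same random effect or family-clustered robust standard errors in the adverse-event regression.
- Add a sensitivity analysis of both endpoints with one member per family, and report how many participants have a relative in the study and in which groups.

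The cost is one data field and one variance term, with no added burden of visits or samples. The drawback is that the family variance may be poorly estimated if few families contribute more than one member, especially in the groups of 5 to 10. In that case the one-member-per-family analysis serves as the check.

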8.4.2 Analysis of the Secondary Endpoints

We will calculate descriptive summaries, stratified by immune deficiency/dysregulation group, for incidence of vaccine-associated AEs listed in the Post-Vaccine Adverse Events questionnaire. Incidence of AEs among immune deficient/dysregulated patients will be compared with incidence among healthy volunteers using regression analyses, possibly adjusting for covariates, such as age and sex, as deemed appropriate.

9 REGULATORY AND OPERATIONAL CONSIDERATIONS

9.1 Informed Consent Process

9.1.1 Consent/Accent Procedures and Documentation

Informed consent is a process where information is presented to enable persons to voluntarily decide whether or not to participate as a research subject. It is an ongoing conversation between the human research participant and the researchers that begins before consent is given and continues until the end of the participant's involvement in the research. Discussions about the research will provide essential information about the study and include purpose, duration, experimental procedures, alternatives, risks, and benefits. Coercion and undue influence will be minimized by informing participants that their decision to join the study will not affect any medical care they are currently receiving, or their eligibility to participate in other research studies at the NIH. Participants will be given the opportunity to ask questions and have them answered.

Informed consent will be obtained via telephone or video conference for participants unable to come to the NIH CC in person or will be obtained in person at the NIH by a study team member authorized to obtain consent. Whether in person or remote, the privacy of the subject will be maintained. Consenting investigators (and participant, when in person) will be located in a private area (eg, clinic consult room). When consent is conducted remotely, the participant will be informed of the private nature of the discussion and will be encouraged to relocate to a more private setting if needed. The participants will sign the informed consent document prior to undergoing any research procedures. The participants may withdraw consent at any time throughout the course of the trial. A copy of the informed consent document will be given to the participants for their records. The researcher will document the signing of the consent form in the participant's study record. The rights and welfare of the participants will be protected by emphasizing to them that the quality of their medical care will not be adversely affected if they decline to participate in this study.

Assent Process: Minor participants will be included in all discussions about the study, and age-appropriate language will be used to describe the procedures and tests involved in this study, along with the risks, discomforts and benefits of participation. Minor participants aged 16 or 17 years will provide assent by signing the informed consent document. Those aged 7 to 15 years will provide assent by signing the assent document. Children under the age of 7 will not be required to provide assent as they typically do not have the ability to fully understand the nature of research. The parent(s)/legal guardian(s) will provide permission for the minor participant to participate by signing the consent form. The consent/assent process will be documented in the child's medical record, including the assessment of the child's ability to provide written assent as applicable.

Remote Consent Process: The informed consent/assent document(s) will be sent via secure email or file transfer to the potential participant and their parents (as applicable) prior to the consent discussion. An explanation of the study will be provided over the telephone or video conference (e.g., Microsoft Teams) after the participant and parents (as applicable) has had the opportunity to read the consent/assent form(s). During the consent process, participants and investigators will view individual copies of the approved consent document on screens at their respective locations. The participant and parents (as applicable) can print the form(s) to sign and date in ink, or they can sign and date digitally with a finger, stylus, or mouse in iMed or Adobe.

The participant will return the signed and dated consent/assent form(s) to the consenting investigator, who will sign and date it with the date it was received. The consent/assent form(s) can either be printed and signed and dated in ink, or signed and dated digitally as described above. A fully executed copy will be sent to the participant for their records.

The informed consent process will be documented on a progress note by the consenting investigator. The investigator will confirm that written consent has been obtained prior to initiating any study interventions.

9.1.2 Considerations for Consent of NIH Staff

Consent for NIH staff will be obtained as detailed above and will comply with the requirements of NIH Human Research Protections Program (HRPP) Policy 404 *Research Involving NIH Staff as Subjects*.

Consent from NIH staff for whom this research is taking place within their own work unit or is conducted by any of their supervisors will, when possible, be obtained by an individual in a non-supervisory relationship with that staff member. When consent of that staff member is conducted, a third party will be present to observe the consent process in order to minimize the risk of undue pressure on the staff member.

9.1.3 Consent for minors when they reach the age of majority

When a pediatric subject reaches age 18, continued participation (including ongoing interactions with the subject or continued analysis of identifiable data) will require that consent be obtained from the now adult with the standard protocol consent document to ensure legally effective informed consent has been obtained.

If reconsent is not feasible, we request waiver of informed consent to continue to use data and/or specimens for those individuals who become lost to follow up or who have been taken off study prior to reaching the age of majority.

Requirements for Waiver of Consent consistent with 45 CFR 46.116 (d):

- (1) The research involves no more than minimal risk to the subjects.
 - a. Analysis of samples and data from this study involves no additional risks to subjects.
- (2) The research could not practicably be carried out without the waiver or alteration.
 - a. Considering the length of time between the minor's last contact with the research team and their age of majority, it will likely be very difficult to locate

them again. A significant reduction in the number of samples analyzed is likely to impact the quality of the research.

- (3) As the research involves using identifiable private information or identifiable biospecimens, the research could not practicably be carried out without using such information or biospecimens in an identifiable format.
 - a. Though the purpose of future studies cannot yet be known, they often involve the correlation of clinical outcomes and clinical interventions with laboratory studies. Such information would be unavailable if access to medical record numbers was unavailable.
- (4) The waiver or alteration will not adversely affect the rights and welfare of the subjects.
 - a. Retention of these samples or data does not affect the welfare of subjects.
- (5) Whenever appropriate, the subjects will be provided with additional pertinent information after participation.
 - a. We only request a waiver of consent for those subjects who have been lost to follow-up or who have been taken off study prior to reaching the age of majority.

The informed consent process will be documented in the medical record.

The investigator will confirm that, when required, written legally effective consent has been obtained prior to initiating any study interventions.

